	
 • Renal failure requiring dialysis, • Hypotension episodes that required continuous vasopressor therapy, • Acute pulmonary oedema, acute respiratory distress syndrome, transfusion-related acute lung injury (TRALI), • Measured and/or estimated volumes of total blood loss, • Blood-collecting containers (if any): date, time and duration of setting and removal, 
Adverse events during the study
 
 • From the signature of the informed consent form to the end of study visit (6 ± 2 weeks after delivery): serious and non-serious AEs whether or not considered to be causally related to the investigational medicinal product (IMP). 
Laboratory parameters (at inclusion, H2, H6, D2):
 
 • Complete blood count, Hb, Ht and platelets • Plasma fibrinogen • Haemostatic profile: PT, QT, aPTT, D-dimers • Plasma creatinine and urea at inclusion and D2 
Prior/Concomitant treatments (total dose, modalities, start and end of administration):
 
 • Prior treatment: all relevant prior medication taken within 7 days before inclusion, including all medication administered since the beginning of the delivery • Concomitant treatments including intravenous fluids, blood products, tranexamic acid and fibrinogen concentrate as rescue therapy

ENDPOINTS AND EVALUATION PARAMETERS
	
Primary endpoint:
 
Percentage of patients losing at least 4 g/dl of Hb, and/or requiring the transfusion of at least 2 units of packed RBCs within the 48 hours following the administration of IMP.
 
The reference for Hb level is the most recent value recorded during the third trimester of pregnancy.
 
Secondary endpoints:
 
 • Evolution of haemorrhage 
 ○ Percentage of patients losing at least 4 g/dl of Hb, 48 hours following the IMP administration, with regards to the Hb reference level. ○ Percentage of patients losing at least 3 g/dl of Hb, 48 hours following the IMP administration, with regards to the Hb reference level. ○ Percentage of patients requiring transfusion of at least 2 units of packed RBCs, 48 hours following the IMP administration. ○ Percentage of patients losing at least 4 g/dl of Hb, 48 hours

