12.3. Sample Size Determination

It is estimated that, in the control group, 42% of patients will fulfil the primary endpoint (unpublished data from the Pithagore cohort). With an expected percentage of patients in the Clottafact[®] treated group of 27%, the difference between the two groups will be of 15%. With a power (1-β) of 90%, a type I error (α) of 5% and a two-sided test (Z test, unpooled variance), a sample size of 206 patients per treatment group is needed.

The rate of drop-out is assumed to be approximately 5%. Therefore, 434 patients will be included in the study.

As there is some uncertainty about the test Z variance depending itself on the expected rates, the variance will be re-estimated in a blind way at 80% of the initially planned sample size (i.e. 80% of 412=326 evaluable patients or 348 patients with adjustment for a 5% dropout rate) and the sample size will be increased according to the new estimated variance so as to maintain the power to 90% while still considering the same originally planned difference in failure rates, i.e. 15%.

It can be shown that the possible increase in sample size with adjustment for a 5% dropout rate cannot exceed 50 additional patients. Therefore, the new sample size will not exceed 484 patients.“

Of note, as the sample size reassessment is performed in a blind way, i.e. based on an overall estimate of the overall failure rate, it is known to not inflate the type I error of the primary analysis. An additional rule for the reassessment of the sample size is as follows: only an increase (i.e. no decrease) in the sample size will be allowed at the blind interim analysis.

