12.4. Randomisation

Treatment units will be pre-numbered and allocated by the Investigator sequentially, in ascending number, and in chronological order of inclusion.

Randomisation will be stratified on the centre using fixed block size and a ratio active treatment/placebo of 1:1.

The randomisation list will be generated with validated SAS program by a subcontractor (not involved in the statistical analysis). LFB BIOMEDICAMENTS keeps a paper copy and an electronic format copy together in a confidential place.

The blindness will be maintained throughout the trial and up to the database lock.

For DSMB activity purpose (if needed), the randomisation list may be transmitted to an independent statistician, external to the sponsor, with high confidentiality.

For details about how blindness is maintained throughout the study, see [Section 3.3](#).

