Handling missing data	12.7. General Rules for Handling of Missing or Inconsistent Data “Concerning the primary efficacy endpoint, missing data (including incomplete dates) will be estimated as failures.”	
SAP: “No imputation of missing data will be proposed for the primary analysis of the primary endpoint. “
 
Rationale for change: There is no best method for handling missing data. The approach for handling missing data as recommended by the EMA guideline on missing data in confirmatory trials (EMA, 2010) should consider various missingness mechanisms along with subsequent analyses.
 
Three methods for handling missing data will be considered.
 
 - The method n°1 considers no replacement of missing data (which is considered as the primary method). - The method n°2 replaces missing data by failures regardless of the randomized treatment (which is considered as a sensitivity method). This method relies on strong assumptions corresponding to a particular MNAR missingness mechanism, and should thus not be envisaged in first place. - The method n°3 (which is considered as another sensitivity method) performs multiple imputations (MI) for missing data, assuming a MAR missingness mechanism. As there is no other post randomization assessment of the primary endpoint when this latter is missing, the multiple imputation process must be based on baseline and post randomization covariates other than intermediate assessments of the primary endpoint. Blinded simulations have shown that important prognostic factors (such as country) could not be fitted as the model could not converge. Hence, this method based on multiple imputations relies on a somewhat subjective choice of covariates and should not be considered as the primary one.
Primary Analysis	12.10.1.2. Primary analysis “The primary model analysis will be an exact logistic regression adjusting for treatment, centre, and baseline fibrinogen (categorized into three classes, ≤ 2 g/L,]2 g/L; 4g/L], > 4 g/L)”	SAP : The primary model of analysis will be a logistic regression to assess the association between a binary exposure variable treatment (variable “_trt”) and the binary outcome (variable “_resp”), adjusting for centre and baseline fibrinogen (variable “_b_fibrinogen”,

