3.3.6.2.2 Model of analysis of the primary endpoint

The primary model of analysis will be a logistic regression to assess the association between a binary exposure variable treatment (variable “_trt”) and the binary outcome (variable “_resp”), adjusting for baseline fibrinogen (variable “_b_fibrinogen”, categorized into four classes (\leq 2 g/L,]2;3] g/L,]3,4] g/L, $>$ 4 g/L) and centre (see SAS code in §7.1). Missing data will be not imputed, assuming the missing completely at random (MCAR) assumption.

The treatment effect (odds ratio of failure) with its 95% confidence interval (95% CIs) will be provided by treatment group and tested at the 5% two-sided level of significance in this model.

Validity of the primary analysis: A graphical analysis of residuals will be done for verifying that assumptions for the primary analysis are met. If adjusting for centre effects lead to convergence issues or unstable estimates, centre effect will be ignored in the analysis.

3.3.6.2.3 *Sensitivity Analyses of the primary endpoint*

3.3.6.2.3.1 Primary sensitivity analysis (MAR assumption)

Assuming the missing at random (MAR) mechanism, multiple imputation (MI) approach by Fully Conditional Specification (FCS) will be used to handle missing data of the primary efficacy endpoint.

A stepwise logistic regression will be done to identify relevant covariates by a backward elimination analysis based on iterative maximum likelihood with the Newton-Raphson algorithm using a significance level of 0.2 to retain variables in the model. Only relevant covariates will be introduced in the MI process. The number of imputations needed will be verified with relative efficiency (RE) for the fully efficient imputation (in unit of variance) and by replicating sets of imputations checking whether the estimates are stable between imputation sets. With a little of missing information (10%), only a small number of imputations are necessary.

The final set of key covariates (referenced here below in the SAS syntax as “key_covariates_for_MI”, see §7.2 for SAS code) to be accounted for in the MI model in addition to treatment and categorized baseline fibrinogen will be defined before breaking the blind.

3.3.6.2.3.2 Secondary sensitivity analysis (MNAR assumption)

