7.2 SAS code fragments for sensitivity analyses (FCS model) of the primary endpoint

The SAS code for MI imputation with FCS model is written as follows:

```

/* Model MI FCS */
Proc MI data= Main_analysis seed =xxx nimpute =100 out = logistic_ficout;
Var _trt centre _b_fibrinogen_ key_covariates_for_MI Resp;
class _trt centre _b_fibrinogen_ key_covariates_for_MI resp;
fcs logistic(resp = _trt centre _b_fibrinogen key_covariates_for_MI
/details) ;
run;
/* PRIMARY MODEL OF ANALYSIS */
proc logistic data = logistic_ficout descending;
class _trt centre _b_fibrinogen(PARAM=REF REF="> 4 g/L") / param=glm;
model _resp = _trt centre _b_fibrinogen /influence iplots;
ods output ParameterEstimates =_ logistic_parms ;
by _imputation_;
run;

```

```

/* COMBINE RESULTS OF MULTIPLE IMPUTATIONS, INFERENCES */
proc mianalyze parms (classvar =classval) = logistic_parms;
class _trt;
modeleffects _trt;
ods output parameterestimates= logistic_outcome;
run;
data res;
set logistic_outcome;
estimate_back=exp(estimate);
lcl_back= exp(estimate -1.96*stderr);
ucl_back= exp(estimate +1.96*stderr);
run;
proc print data= res;run;

```

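### MCAR cannot justify the complete-case primary analysis of this and/or composite, and the MAR sensitivity analysis leaves out the H2 and H6 haemoglobin and fits an outcome variable it did not impute

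*SAP*

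**What the plan says.** **Endpoint.** SAP 1.10.1 defines failure as a loss of at least 4 g/dL of haemoglobin from the third-trimester reference, and/or transfusion of at least two red-cell units, within 48 hours. SAP 3.3.3 treats the endpoint as missing only when it cannot be evaluated. Before that, a haemoglobin taken outside the study within 48 hours of inclusion may be substituted, and the scientific committee confirms each missing case.

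**Primary analysis.** SAP 3.3.6.2.2 fits a logistic model on complete cases: "Missing data will be not imputed, assuming the missing completely at random (MCAR) assumption". Protocol 12.7 had counted missing endpoints as failures, whereas the protocol synopsis says they are not replaced. SAP 2.2 records only the departure from 12.7.

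**Sensitivity analyses.** The first is multiple imputation under MAR (SAP 3.3.6.2.3.1). The second counts all missing endpoints as failures (3.3.6.2.3.2). SAP 2.2 explains why the imputation must use covariates other than intermediate assessments of the primary endpoint: "As there is no other post randomization assessment of the primary endpoint when this latter is missing".

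**Haemoglobin schedule.** The protocol synopsis lists "Laboratory parameters (at inclusion, H2, H6, D2", and protocol 8.2.3 and 8.2.4 repeat the H2 and H6 blood counts. SAP 3.3.6.3.2.2.1 models haemoglobin at H2, H6 and D2.

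**Code.** In SAP 7.2 the imputation statement is "fcs logistic(resp = _trt centre _b_fibrinogen key_covariates_for_MI". The logistic step that follows fits `_resp`.

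**The concern.** The stated justification for the primary analysis conflicts with the endpoint definition. If the record shows two or more units, the composite is known. If it shows fewer, the composite is known only when haemoglobin is available. A failure therefore has two ways of being observed and a non-failure has one, which is not MCAR.

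The analysis meant to test this assumption is weaker than the data allow. When the D2 haemoglobin is missing, the natural predictors of it are the haemoglobins measured hours earlier in the same woman. The post-randomisation covariates in SAP 3.3.6.1.2 include plasma, platelets, balloon, intensive-care transfer and heart rate, but neither H2 or H6 haemoglobin nor red-cell units. Inclusion haemoglobin enters only as a yes/no loss of 2 g/dL.

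At stake are the raw failure percentages by arm and the value of the main robustness check.

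**Working it through.** **1. The plan's own figure.** Protocol 12.3 gives "in the control group, 42% of patients will fulfil the primary endpoint", "treated group of 27%, the difference between the two groups will be of 15" points, and "With a power (1-β) of 90%, a type I error (α) of 5% and a two-sided test (Z test, unpooled variance". Then n = (1.960 + 1.282)² × (0.42×0.58 + 0.27×0.73) / 0.15² = 10.507 × 0.4407 / 0.0225 = 205.8, so 206 per group as stated. The true odds ratio at these rates is (0.27/0.73)/(0.42/0.58) = 0.511. These rates are used below.

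**2. Inputs the documents do not give.**
- m, the share of women without a usable haemoglobin. Assumed 5% (the figure used for dropout) and 10% (the missing-information figure in the imputation text, which is not a forecast of missing endpoints). SAP 1.11 implies 448 × (1 − 0.0155) = 441 women analysed, so 5% and 10% are about 22 and 44 women.
- s, the share of failures with two or more units. Assumed 25% to 75%.

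**3. Who is observed.** Suppose haemoglobin is missing purely at random. All non-failures have fewer than two units, so:
- P(observed | failure) = 1 − m(1 − s)
- P(observed | non-failure) = 1 − m

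With s = 50%, failures are missing at 2.5% and non-failures at 5% (m = 5%), or 5% and 10% (m = 10%). Missingness of the endpoint depends on outcome even when missingness of haemoglobin does not.

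**4. Effect on the odds ratio.** Let k = P(observed | failure) / P(observed | non-failure) in each arm. Then OR(complete case) = OR(true) × k(active) / k(placebo). If k is the same in both arms, the odds ratio is unchanged. The fibrinogen and centre terms of the logistic model similarly absorb differences between strata.

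| m | s placebo | s active | Placebo rate | Active rate | OR |
|---|---|---|---|---|---|
| none missing | – | – | 42.0% | 27.0% | 0.511 |
| 5% | 50% | 50% | 42.6% | 27.5% | 0.511 |
| 10% | 50% | 50% | 43.3% | 28.1% | 0.511 |
| 5% | 75% | 25% | 42.9% | 27.3% | 0.498 |
| 5% | 25% | 75% | 42.3% | 27.8% | 0.524 |
| 10% | 75% | 25% | 44.0% | 27.5% | 0.485 |
| 10% | 25% | 75% | 42.7% | 28.6% | 0.538 |

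For example, with m = 10%, s = 75% (placebo) and 25% (active): 0.511 × 0.925/0.975 = 0.485.

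**5. Limits when missingness also depends on haemoglobin.** Here 5% or 10% of endpoints are missing in each arm.
- All missing women are non-failures: 0.42/0.95 = 44.2% and 0.27/0.95 = 28.4%, OR 0.501. At 10%: 46.7% and 30.0%, OR 0.490.
- Missing women all fail in one arm and none fail in the other: OR 0.380 to 0.622 at 5%, and 0.266 to 0.777 at 10%. These are bounds, not expectations.

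**6. Missing counted as failure.** The rate becomes p + m(1 − p). At m = 5%: 44.9% and 30.65%, OR 0.542. At 10%: 47.8% and 34.3%, OR 0.570.

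**7. The imputation code.** SAP 7.1 shows `_resp` in `Main_analysis`, the dataset that SAP 7.2 passes to the imputation. There are two cases. If `resp` is also in that dataset, `resp` is imputed, `_resp` keeps its gaps, and all 100 logistic fits repeat the complete-case result. If it is not, the imputation step stops with an error. In neither case is the imputed outcome analysed.

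**The case against.** **The SAP does not deny that intermediate haemoglobin exists.** A reader might infer that it does. The sentence denies only another assessment of the primary endpoint, which belongs to H48 with a window of H32 to H52. That objection stands. The fault is narrower: a missing composite is no reason to leave out earlier measurements of one of its components.

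**The primary result is barely touched.** A reader might infer that a false MCAR claim biases the treatment effect. It need not. The primary measure is an odds ratio, and step 4 shows it unchanged when missingness depends on outcome alike in both arms. The imputation is only a sensitivity analysis. This also stands.

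**Missing endpoints may be few.** The off-study haemoglobin, the blinded confirmation of missing cases, and the fixing of imputation covariates before unblinding all help. They reduce the size of the problem but do not make MCAR true.

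**Transfusion status may be missing too**, for example when a woman refuses use of her data. That is correct, so the argument is confined to women whose transfusion record is known.

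**Leaving red-cell units out of a binary imputation is defensible**, because two or more units predicts failure perfectly and the logistic imputation would separate. That is a reason to impute haemoglobin rather than the composite.

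**The code is a fragment read from a PDF.** Other names in it also disagree (`_b_fibrinogen_` against `_b_fibrinogen`), so lost characters are possible. However, the line that imputes `resp` keeps the underscore on `_trt`. The discrepancy should be checked against the program.

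**Conclusion.** The point holds in a limited form. MCAR is incompatible with the endpoint definition as soon as any endpoint is missing for want of a haemoglobin. Raw failure percentages would tend to be too high: by 0.5 to 1.3 points at 5% to 10% missing with half of failures transfused, and by at most 2.2 points (5%) or 4.7 points (10%) if every missing woman is a non-failure.

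The odds ratio is preserved when k is equal across arms. It shifts to between 0.485 and 0.538 under strongly unequal transfusion shares at 10% missing. Only outcome-dependent missingness that runs in opposite directions by arm could move it far. The missing rates and transfusion shares are assumptions, because the documents give neither.

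The MAR analysis leaves out its most relevant measurements on a rationale that does not support doing so, and as printed it does not analyse the imputed outcome. A reader might go further and infer that neither sensitivity analysis brackets the truth. The documents do not support that: the final imputation covariates are not stated, and no correlation between H6 and D2 haemoglobin is given, so the result of the planned imputation cannot be worked out.

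**What to change.** 1. In SAP 3.3.6.2.2, replace the MCAR statement with the assumption actually needed: given the model covariates, missingness is not related to outcome differently by arm.
2. In the MAR sensitivity analysis, impute the continuous D2 haemoglobin from treatment, centre, baseline fibrinogen, the reference, inclusion, H2 and H6 haemoglobins, and red-cell units. Then derive the composite, with known transfusion failures fixed as failures.
3. Correct the rationale in SAP 2.2 to say that the composite has no intermediate assessment but its haemoglobin component does.
4. Use one outcome name throughout the imputation and logistic code in SAP 7.2.
5. Report the number of missing endpoints by arm.

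The cost is SAP wording and modest programming. Every variable is already scheduled for collection, and the primary test does not change.
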